5.3.5 Procedures for Recording Adverse Events

Investigators should use correct medical terminology/concepts when recording adverse events on the Adverse Event eCRF. Avoid colloquialisms and abbreviations.

Only one adverse event term should be recorded in the event field on the Adverse Event eCRF.

5.3.5.1 Infusion-Related Reactions

Adverse events that occur during or within 24 hours after study drug administration and are judged to be related to study drug infusion should be captured as a diagnosis (e.g., “infusion-related reaction” or “anaphylactic reaction”) on the Adverse Event eCRF. If possible, avoid ambiguous terms such as “systemic reaction.” Associated signs and symptoms should be recorded on the dedicated Infusion-Related Reaction eCRF. If a patient experiences both a local and systemic reaction to the same dose of study drug, each reaction should be recorded separately on the Adverse Event eCRF, with signs and symptoms also recorded separately on the dedicated Infusion-Related Reaction eCRF.

Investigators should consider a local IRR for any symptoms affecting the skin and localized to only one place. Any other IRR should be considered systemic.

Further details on prevention and management of IRRs are described in Section 5.1.3.1.1, Section 5.1.4 (Table 2), and in the Ocrelizumab Investigator’s Brochure.

Ocrelizumab—Genentech, Inc.
50/ Protocol MN30035, Version 5

5.3.5.2 Diagnosis versus Signs and Symptoms

For adverse events, a diagnosis (if known) should be recorded on the Adverse Event eCRF rather than individual signs and symptoms (e.g., record only liver failure or hepatitis rather than jaundice, asterixis, and elevated transaminases).

5.3.5.3 Adverse Events That Are Secondary to Other Events

In general, adverse events that are secondary to other events (e.g., cascade events or clinical sequelae) should be identified by their primary cause, with the exception of severe or serious secondary events. A medically significant secondary adverse event that is separated in time from the initiating event should be recorded as an independent event on the Adverse Event eCRF. For example:

- If vomiting results in mild dehydration with no additional treatment in a healthy adult, only vomiting should be reported on the eCRF.
- If vomiting results in severe dehydration, both events should be reported separately on the eCRF.
- If a severe gastrointestinal hemorrhage leads to renal failure, both events should be reported separately on the eCRF.
- If dizziness leads to a fall and consequent fracture, all three events should be reported separately on the eCRF.
- If neutropenia is accompanied by an infection, both events should be reported separately on the eCRF.

All adverse events should be recorded separately on the Adverse Event eCRF if it is unclear as to whether the events are associated.

5.3.5.4 Persistent or Recurrent Adverse Events

A persistent adverse event is one that extends continuously, without resolution, between patient evaluation timepoints. Such events should only be recorded once on the Adverse Event eCRF. The initial severity (intensity or grade) of the event will be recorded at the time the event is first reported. If a persistent adverse event becomes more severe, the most extreme severity should also be recorded on the Adverse Event eCRF. If the event becomes serious, it should be reported to the Sponsor immediately (i.e., no more than 24 hours after learning that the event became serious; see Section 5.4.2 for reporting instructions). The Adverse Event eCRF should be updated by changing the event from "non-serious" to "serious," providing the date that the event became serious, and completing all data fields related to serious adverse events.

A recurrent adverse event is one that resolves between patient evaluation timepoints and subsequently recurs. Each recurrence of an adverse event should be recorded as a separate event on the Adverse Event eCRF.

5.3.5.5 Abnormal Laboratory Values

Not every laboratory abnormality qualifies as an adverse event. A laboratory test result must be reported as an adverse event if it meets any of the following criteria:

- Is accompanied by clinical symptoms
- Results in a change in study treatment (e.g., dosage modification, treatment interruption, or treatment discontinuation)
- Results in a medical intervention (e.g., potassium supplementation for hypokalemia) or a change in concomitant therapy
- Is clinically significant in the investigator's judgment

It is the investigator's responsibility to review all laboratory findings. Medical and scientific judgment should be exercised in deciding whether an isolated laboratory abnormality should be classified as an adverse event.

If a clinically significant laboratory abnormality is a sign of a disease or syndrome (e.g., alkaline phosphatase and bilirubin 5 \times ULN associated with cholestasis), only the diagnosis (i.e., cholestasis) should be recorded on the Adverse Event eCRF.

If a clinically significant laboratory abnormality is not a sign of a disease or syndrome, the abnormality itself should be recorded on the Adverse Event eCRF, along with a descriptor indicating whether the test result is above or below the normal range (e.g., "elevated potassium," as opposed to "abnormal potassium"). If the laboratory abnormality can be characterized by a precise clinical term per standard definitions, the clinical term should be recorded as the adverse event. For example, an elevated serum potassium level of 7.0 mEq/L should be recorded as "hyperkalemia."

Observations of the same clinically significant laboratory abnormality from visit to visit should only be recorded once on the Adverse Event eCRF (see Section 5.3.5.4 for details on recording persistent adverse events).

5.3.5.6 Abnormal Vital Sign Values

Not every vital sign abnormality qualifies as an adverse event. A vital sign result must be reported as an adverse event if it meets any of the following criteria:

- Is accompanied by clinical symptoms
- Results in a change in study treatment (e.g., dosage modification, treatment interruption, or treatment discontinuation)
- Results in a medical intervention or a change in concomitant therapy
- Is clinically significant in the investigator's judgment

It is the investigator's responsibility to review all vital sign findings. Medical and scientific judgment should be exercised in deciding whether an isolated vital sign abnormality should be classified as an adverse event.

If a clinically significant vital sign abnormality is a sign of a disease or syndrome (e.g., high blood pressure), only the diagnosis (i.e., hypertension) should be recorded on the Adverse Event eCRF.

Observations of the same clinically significant vital sign abnormality from visit to visit should only be recorded once on the Adverse Event eCRF (see Section 5.3.5.4 for details on recording persistent adverse events).

5.3.5.7 Abnormal Liver Function Tests

The finding of an elevated ALT or AST ($>3 \times \text{ULN}$) in combination with either an elevated total bilirubin ($>2 \times \text{ULN}$) or clinical jaundice in the absence of cholestasis or other causes of hyperbilirubinemia is considered to be an indicator of severe liver injury (as defined by Hy's law). Therefore, investigators must report as an adverse event the occurrence of either of the following:

- Treatment-emergent ALT or AST $>3 \times \text{ULN}$ in combination with total bilirubin $>2 \times \text{ULN}$
- Treatment-emergent ALT or AST $>3 \times \text{ULN}$ in combination with clinical jaundice

The most appropriate diagnosis or (if a diagnosis cannot be established) the abnormal laboratory values should be recorded on the Adverse Event eCRF (see Section 5.3.5.2) and reported to the Sponsor immediately (i.e., no more than 24 hours after learning of the event), either as a serious adverse event or an adverse event of special interest (see Section 5.4.2).

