5.2.3 Adverse Events of Special Interest (Immediately Reportable to the Sponsor)

Adverse events of special interest are required to be reported by the investigator to the Sponsor immediately (i.e., no more than 24 hours after learning of the event; see Section [5.4.2](#) for reporting instructions). Adverse events of special interest are identified for ocrelizumab in the indicated patient population in Section [5.1.3.1](#). Standard adverse events of special interest include the following:

- Cases of potential drug-induced liver injury that include an elevated ALT or AST in combination with either an elevated bilirubin or clinical jaundice, as defined by Hy's law (see Section [5.3.5.7](#)).
- Suspected transmission of an infectious agent by the study drug, as defined below:
Any organism, virus, or infectious particle (e.g., prion protein transmitting transmissible spongiform encephalopathy), pathogenic or non-pathogenic, is considered an infectious agent. A transmission of an infectious agent may be suspected from clinical symptoms or laboratory findings that indicate an infection in a patient exposed to a medicinal product. This term applies only when a contamination of the study drug is suspected.

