## **STATISTICAL ANALYSIS PLAN AMENDMENT RATIONALE**

**April 2019**

In this version of Statistical Analysis Plan (SAP), updates have been made following the approval of version 1 of the SAP:

- Study design section has been updated to reflect the protocol version 5 updates including removing the B cell monitoring after Week 96, and the shorter infusion substudy.
- Analysis plan of the shorter infusion substudy was added in [Appendix 6](#).
- Sensitivity analysis plan of the primary endpoint has been specified including per protocol analysis and sensitivity analysis for missing data.
- Preferred terms of the AESIs (AE of Special Interest) have been updated per MedDRA coding latest version.

Additional minor changes have been made to improve clarity and consistency.

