#### **4.7.3 Laboratory Data**

Associated laboratory parameters, such as hepatic function, renal function, and hematology values, will be grouped and presented together. A summary of the number and percentage of patients with abnormal laboratory outcomes will be produced for each parameter.

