#### **4.7.5 Safety Endpoints of Special Interest**

All reported AESI will be summarized overall and by NCI CTCAE v4.0 grade, and tabulated by specific MedDRA bucket terms and preferred terms. The following types of events are of special interest:

- Drug-induced liver injury
- Suspected transmission of an infectious agent via product

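### The SAP never applies the protocol's combined criterion for potential drug-induced liver injury, so a qualifying case may be absent from the liver-injury AESI count

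*Protocol*

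**What the plan says.** Protocol 5.2.3 makes this one of the standard adverse events of special interest: "Cases of potential drug-induced liver injury that include an elevated ALT or AST in combination with either an elevated bilirubin or clinical jaundice". Protocol 5.3.5.7 sets the limits: ALT or AST above 3 x ULN with total bilirubin above 2 x ULN "or clinical jaundice in the absence of cholestasis or other causes of hyperbilirubinemia is considered to be an indicator of severe liver injury". Investigators must report either combination when it is treatment-emergent.

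On what is written down, 5.3.5.7 says: "The most appropriate diagnosis or (if a diagnosis cannot be established) the abnormal laboratory values should be recorded on the Adverse Event eCRF". Protocol 5.3.5.2 gives the general rule with a liver example: "record only liver failure or hepatitis rather than jaundice, asterixis, and elevated transaminases". On the route, 5.3.5.7 has the case sent "either as a serious adverse event or an adverse event of special interest".

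SAP 4.7.5 names drug-induced liver injury as one of two event types of special interest and plans this: "All reported AESI will be summarized overall and by NCI CTCAE v4.0 grade, and tabulated by specific MedDRA bucket terms and preferred terms". The SAP amendment rationale adds: "Preferred terms of the AESIs (AE of Special Interest) have been updated per MedDRA coding latest version". The term list itself is not in the supplied SAP. For the laboratory data, SAP 4.7.3 shows hepatic parameters as a group and then plans: "A summary of the number and percentage of patients with abnormal laboratory outcomes will be produced for each parameter".

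**The concern.** The protocol's definition is a conjunction within one patient: a raised transaminase and either raised bilirubin or jaundice. The SAP's two outputs work on something else. One counts reports by their coded term, and the other counts abnormal results by parameter. The protocol also directs qualifying cases to different terms (hepatitis, liver failure, the bare laboratory values) and offers two reporting routes.

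The count for one of only two AESI types therefore rests on how a case was reported and coded, and the data that would check it directly are not used for that purpose. With a rare event, one case left out of the row can be the difference between stating that none was observed and stating that one was.

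**Working it through.** **Inputs.** Definition and thresholds: Protocol 5.2.3 and 5.3.5.7. Recording rule: Protocol 5.3.5.2 and 5.3.5.7. Analyses: SAP 2.2.5, 4.7.2, 4.7.3 and 4.7.5. Laboratory panel: Protocol 4.5.8. Visit days: Protocol Appendix 1. Planned N of about 600: Protocol 3.7. The plan states no liver-event rate or count, so it has no figure to reproduce on this point.

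**1. Can the per-parameter counts recover the combined count?** With *a* patients above the transaminase limit, *b* above the bilirubin limit and *N* in all, the joint count lies between max(0, *a* + *b* − *N*) and min(*a*, *b*). Assume *a* = *b* = 5 and *N* = 600. The lower bound is max(0, −590) = 0 and the upper bound is 5. Any value from 0 to 5 fits. Showing hepatic parameters together in one display does not narrow this. SAP 4.7.3 also gives no threshold for an abnormal result, so its counts need not be at 3 x or 2 x ULN.

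**2. Does the AESI summary contain every qualifying case?** SAP 4.7.5 can be read in two ways.

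- *Records marked as AESI by the site.* A marked case recorded as hepatitis is included. A case sent only as an SAE, without the AESI mark, is not.
- *Records matched to a MedDRA term list.* If all AE and SAE records are searched, an SAE with a listed term is found. A case whose diagnosis is not on the list is not found.

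These are alternatives, so the two gaps do not add up. Each reading still leaves a way for a qualifying case to stay out of the row, and the SAP does not say which reading applies.

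**3. Scale.** Exact (Clopper-Pearson) 95% intervals; the same function returns (0.03, 5.45)% for 1/100, matching the substudy sample-size table.

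- 0/600: 0%. Upper limit 1 − 0.025^(1/600) = 0.61%.
- 1/600: 0.17% (0.004% to 0.93%).
- 2/600: 0.33% (0.04% to 1.20%).

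One case raises the upper limit from 0.613% to 0.925%, a factor of 0.925/0.613 = 1.5. For an assumed true rate of 0.05% to 0.5%, the expected number in 600 is 0.3 to 3.0. The chance of at least one case, 1 − (1 − p)^600, is 26% to 95%.

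**4. Which samples may be paired?** Scheduled chemistry after baseline falls on Days 169, 337, 505 and 673, so consecutive samples are 337 − 169 = 168 days apart. Pairing an ALT rise with bilirubin at the next scheduled visit would join results about 24 weeks apart and could create false cases. The pairing has to be within one sample or a short window.

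**5. Can the qualifier about other causes be programmed?** The scheduled panel has AST, ALT, GGT and total bilirubin but no alkaline phosphatase. Cholestasis and other causes cannot be excluded from it, so a programmed flag can only find potential cases.

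**The case against.** The strongest reply is that such a case is not lost. SAP 4.7.2 tabulates all treatment-emergent events by preferred term and summarises Grade 3 to 5 events and SAEs, and Protocol 6.6.2 lists all SAEs. This stands. A reader might infer that a qualifying case disappears from the report, and the documents do not support that. What can be lost is its place in the liver-injury count. In the general tables it is one preferred term, with no link to the patient's bilirubin.

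A reader might also infer that reporting as an SAE is enough to exclude a case. It is not. The protocol defines SAE and AESI separately and does not make them mutually exclusive, both go onto the same Adverse Event eCRF, and a term search over all records would find an SAE with a listed term.

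Nor do the documents show that hepatitis or raised ALT falls outside the liver term list, because the list was not supplied. Some data-handling rules are in DAP Module 2, also not supplied, and a combined display there cannot be ruled out.

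It would also be wrong to say that the laboratory analysis ignores baseline: SAP 2.2.5 includes changes from baseline for AST, ALT and total bilirubin. Those changes are still per parameter.

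Finally, the investigator applies the combined rule when reporting, so a correctly reported AESI already carries it. That is true, but the SAP has no check from the data that every patient meeting the rule was reported and counted.

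**Conclusion.** The point holds in a limited form. The protocol defines potential liver injury by a combined criterion, no analysis in the supplied SAP applies it, and the planned outputs cannot be combined to give the count. A qualifying case may be absent from the liver-injury AESI row while still appearing elsewhere. Whether that would happen depends on how AESIs are identified and on a term list that the supplied documents do not show.

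The size is modest. The study is single-arm and mostly descriptive, no liver-event rate is given, and the intervals above only show how much one case in about 600 moves a rare count. No efficacy result and no sample-size figure changes. This is a cheap improvement to safety reporting.

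**What to change.** In SAP 4.7.5:

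1. State how liver-injury AESIs are identified, give the term list, and apply the rule to all AE and SAE records whatever the reporting route.
2. Add a patient-level flag for ALT or AST above 3 x ULN after the first infusion, with either total bilirubin above 2 x ULN or a reported jaundice event. Take the bilirubin from the same sample, or from a short pre-stated window that uses unscheduled samples and never the next 24-weekly visit.
3. List every flagged or reported case with its pre-dose values, reconcile it to the AE and SAE records, and label it a potential case for medical review.

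The pre-dose values matter because patients may enter with ALT or AST just under 3 x ULN. The reconciliation matters because sites are told to record hepatitis in place of jaundice, so a search for jaundice terms alone will not find every case under that limb.

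The cost is one derived flag and one listing from data already collected. The downside is that some flagged cases may prove to have another cause.

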5.3.5.8 Deaths

All deaths that occur during the protocol-specified, adverse event, reporting period (see Section 5.3.1), regardless of relationship to study drug, must be recorded on the Adverse Event eCRF and immediately reported to the Sponsor (see Section 5.4.2). This includes death attributed to progression of RRMS.

Death should be considered an outcome and not a distinct event. The event or condition that caused or contributed to the fatal outcome should be recorded as the single medical concept on the Adverse Event eCRF. Generally, only one such event should be reported. The term "**sudden death**" should be used only for the occurrence of an abrupt and unexpected death due to presumed cardiac causes in a patient with or without preexisting heart disease, within 1 hour after the onset of acute symptoms or, in the case of an unwitnessed death, within 24 hours after the patient was last seen alive and stable. If the cause of death is unknown and cannot be ascertained at the time of reporting, "**unexplained death**" should be recorded on the Adverse Event eCRF. If the cause of death later becomes available (e.g., after autopsy), "unexplained death" should be replaced by the established cause of death.

If the death is attributed to progression of RRMS, "RRMS progression" should be recorded on the Adverse Event eCRF.

Ocrelizumab—Genentech, Inc.
53/ Protocol MN30035, Version 5

5.3.5.9 Preexisting Medical Conditions

A preexisting medical condition is one that is present at the screening visit for this study. Such conditions should be recorded on the General Medical History and Baseline Conditions eCRF.

A preexisting medical condition should be recorded as an adverse event only if the frequency, severity, or character of the condition worsens during the study. When recording such events on the Adverse Event eCRF, it is important to convey the concept that the preexisting condition has changed by including applicable descriptors (e.g., "more frequent headaches").

5.3.5.10 Lack of Efficacy or Worsening of Relapsing Remitting Multiple Sclerosis

Events that are clearly consistent with the expected pattern of progression of the underlying disease should not be recorded as adverse events. These data will be captured as efficacy assessment data only. In most cases, the expected pattern of progression will be based on EDSS score. In rare cases, the determination of clinical progression will be based on symptomatic deterioration. However, every effort should be made to document progression through use of objective criteria. If there is any uncertainty as to whether an event is due to disease progression, it should be reported as an adverse event.

5.3.5.11 Hospitalization or Prolonged Hospitalization

Any adverse event that results in hospitalization (i.e., in-patient admission to a hospital) or prolonged hospitalization should be documented and reported as a serious adverse event (per the definition of serious adverse event in Section 5.2.2), except as outlined below.

The following are not considered serious adverse events:

- Elective hospitalizations or surgical procedures that are a result of a patient's pre-existing condition(s) that have not worsened since receiving trial medication. Examples may include, but are not limited to, cholecystectomy for gallstones and diagnostic testing. Such events should still be recorded as medical procedures in the concomitant procedures/treatments eCRF.
- Hospitalization to receive trial medication, such as infusions of ocrelizumab, unless this is prolonged (more than 24 hours)
- Hospitalization following an MS relapse as long as the reason for hospitalization is to receive standard treatment with IV methylprednisolone

The following hospitalization scenarios are not considered to be serious adverse events, but should be reported as adverse events instead:

- Hospitalization that was necessary because of patient requirement for outpatient care outside of normal outpatient clinic operating hours

5.4 IMMEDIATE REPORTING REQUIREMENTS FROM INVESTIGATOR TO SPONSOR

Certain events require immediate reporting to allow the Sponsor to take appropriate measures to address potential new risks in a clinical trial. The investigator must report such events to the Sponsor immediately; under no circumstances should reporting take place more than 24 hours after the investigator learns of the event. The following is a list of events that the investigator must report to the Sponsor within 24 hours after learning of the event, regardless of relationship to study drug:

- Serious adverse events (see Section [5.4.2](#) for further details)
- Adverse events of special interest (see Section [5.4.2](#) for further details)
- Pregnancies (see Section [5.4.3](#) for further details)

The investigator must report new significant follow-up information for these events to the Sponsor immediately (i.e., no more than 24 hours after becoming aware of the information). New significant information includes the following:

- New signs or symptoms or a change in the diagnosis
- Significant new diagnostic test results
- Change in causality based on new information
- Change in the event's outcome, including recovery
- Additional narrative information on the clinical course of the event

Investigators must also comply with local requirements for reporting serious adverse events to the local health authority and IRB/EC.

